11 STATISTICAL CONSIDERATIONS

11.1 Method of Randomisation

Patient participants who give their informed consent will complete baseline processes and outcome measures before being individually randomised. The randomisation will be performed by the site team using 24 hour web based randomisation system to protect against subversion whilst ensuring that the trial maintains good balance to the allocation ratio of 1:1 both within each stratum and across the trial. Participants will be stratified by: (1) site and (2) gender. Randomisation will be requested by and will be archived by secure web access to the remote randomisation centre at the CTRC. This system will be set up, maintained and monitored independently of the trial statistician or other trial staff.

11.2 Sample Size calculation

The results from the phase II feasibility trial informed the sample size calculation. The adjusted mean difference in the primary outcome measure (NEADL) between the intervention and control group in the feasibility trial was three. Work completed by Wu, et al ³⁰ has suggested that the minimum clinically significant difference is 2.4, so this has been used within the sample size calculation for this phase III RCT. A two-point score in the NEADL scale would equate to an improvement in function from being independent around the home to being able to use public transport or get in and out of a car. The adjusted mean difference between the groups in NEADL in the randomised feasibility trial had a standard deviation of 5.8. In this phase III RCT a more diverse sample would be expected with breadth in terms of geography, health care pathways, and populations, so a larger SD would be expected. Parker, et al. ³¹ used NEADL in a RCT comparing a rehabilitation intervention for older people in a day hospital compared with rehabilitation at home and found a SD of 10. Based on ANCOVA with alpha of 5% and 90% power to detect a difference of 2.4 (SD = 10, R² of covariate = 0.52) 352 patient participants would be required to complete the trial over both treatment groups. When considering the 79% retention rate, the trial would need to recruit 446 patient participants.

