3 INTRODUCTION

3.1 Background

Proximal femoral fracture, more commonly referred to as hip fracture, is a common, major health problem in old age. The total number of patients entered onto the national hip fracture database in England, Wales and Northern Ireland in 2015 was 65,645¹. As the population ages the number of elderly people falling and fracturing their hips is projected to increase further^{2,3}. Such fractures are strongly associated with decreased bone mineral density, increased age, prior fragility fracture, cognitive impairment, under-nutrition, frailty, poor physical functioning, vision problems, weight loss and other health problems⁴. Mortality is high with 14-58% dying within the following 12 months^{5,6}. A review of the long-term disability associated with proximal femoral fracture found that 29% did not regain their level of functioning after one year in terms of restrictions of activities of daily living⁷. Many who were living independently before their fracture lost their independence afterwards. This imposes a large cost burden on society amounting to about £2.3 billion a year in the United Kingdom equating to approximately £6 million a dav⁸. Tian et al.⁹ explored Torbay's (Devon) unique patient-level linked data set of National Health Service (NHS) and social care costs for older people in the 12 months before and after being admitted to hospital as a result of a fall. They found that the cost of hospital, community and social care cost services for each patient were almost four times as costly in the 12 months after admission, compared with the costs of the admission itself, and that the majority of costs occurred outside of the acute hospital setting. Particularly frail individuals may go onto have a further proximal femoral fracture resulting in additional disability and deaths¹⁰.

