3.2.2 Summary of Phase II Methods

The second phase of the trial assessed the feasibility and acceptability of the intervention; the enhanced rehabilitation package (intervention components outlined in figure 1) in a cohort study of all hip fracture patients with an embedded randomised feasibility trial and further focus groups of rehabilitation teams, patients and carers²⁸. This trial assessed the feasibility of methods for a future definitive parallel-group randomised controlled trial (RCT) and economic evaluation. Participants in the feasibility trial were recruited from three acute hospitals in North Wales, and the rehabilitation intervention was delivered in the community. Participants were older adults aged 65 years or older who had received surgical treatment for hip fracture, had been living independently prior to the hip fracture, had mental capacity as assessed by their clinical team, and received rehabilitation in the North Wales area. Participants were randomised using a remote method to usual care (control) or usual care plus the enhanced rehabilitation package (intervention), which included up to six additional home-based physiotherapy sessions delivered by a physiotherapist or technical instructor. a novel information workbook and a goal-setting diary. For this feasibility trial, the primary outcome measure was the Barthel Activities of Daily Living scale (BADL). Secondary measures included: the Nottingham Extended Activities of Daily Living scale (NEADL), EuroQol EQ-5D, ICECAP capability, Hospital Anxiety and Depression Scale (HADS), visual analogue scale for hip pain intensity, General Self-Efficacy Scale, Falls Efficacy Scale - International (FES-I), Self-Efficacy for Exercise scale, visual analogue scale for fear of falling, tests of physical function and the Clinical Service Receipt Inventory. Outcome measures were assessed at baseline and 3-month follow-up by blinded researchers.

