4 TRIAL DESIGN

This is a pragmatic multisite randomised controlled trial (RCT). This will be a parallel-group, twoarmed, superiority RCT, with 1:1 allocation ratio, stratified by gender and site. The experiences in a Phase II randomisation feasibility trial (section 3.2.3) have been used to inform the design of this trial and furthermore there is an internal pilot phase to assess trial feasibility (section 4.1). Blinded outcome assessment and statistical analysis; unblinded patient and carer participants and clinicians. Economic evaluation will be a cost-utility analysis from a health service and personal social care perspective.

An internal pilot will assess recruitment and retention for the 6 months after the first site has been opened to recruitment. Results from the phase II feasibility trial found that the rate of recruitment for those eligible and invited to participate was 32% (95% CI 26 to 39%), and retention rate was 79% (95% CI 69 to 89%). The monthly recruitment target per site will be 3.25 participants (again based on the feasibility trial recruitment rates).

The progression criteria from the internal pilot phase to the main trial will be in terms of stop, amend or go. All progression criteria should be met or amended as needed before progression to the main trial. The progression criteria are as follows:

Progression Criteria	Go	Amend	Stop
Sites open	7 sites or more	5-6 sites	4 sites or fewer
Open site recruitment rate per month	2 or more participants	1-2 participants	Fewer than 1 participant
Retention rate*	69% or higher	50-68%	49% or lower

* Rates will be rounded to the nearest whole number before applying the progression criteria

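### The 79% retention behind the target of 446 was observed at 3 months, and no retention rate is stated or justified for the 52-week primary endpoint

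*Protocol*

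**What the plan says.** Section 11.2 sets the calculation out as follows: "Based on ANCOVA with alpha of 5% and 90% power to detect a difference of 2.4", with "SD = 10, R² of covariate = 0.52) 352 patient participants would be required to complete the trial over both treatment groups". It then inflates for attrition: "When considering the 79% retention rate, the trial would need to recruit 446 patient participants".

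The source of the 79% is the phase II feasibility trial. Section 3.2.3.1 lists nine withdrawals and four patients who could not be contacted among the 62 recruited. Section 3.2.2 gives the timing: "Outcome measures were assessed at baseline and 3-month follow-up by blinded researchers". No later follow-up of that trial is described.

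Sections 3.3.1 and 11.4 place the primary comparison at 52 weeks. On what may happen between those times, section 3.1 says "Mortality is high with 14-58% dying within the following 12 months". Section 12.2 adds that no further data are collected from a participant who has lost capacity unless it is regained.

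Section 4 provides an early check: "An internal pilot will assess recruitment and retention for the 6 months after the first site has been opened to recruitment". The Go level for retention is 69% or higher. The section also quotes the feasibility retention as 79% with a 95% confidence interval of 69 to 89%.

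**The concern.** An attrition allowance should describe the proportion of randomised participants who will supply the primary outcome at its own time point. Here the allowance comes from a follow-up at about one quarter of that time and is carried over without adjustment or comment. Section 11.2 does not mention that the figure is a 3-month one, so anyone reading that section alone would take 79% to be an estimate for the trial's own endpoint.

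The likely direction of error is clear from the protocol. Losses to death, incapacity and withdrawal accumulate. The feasibility losses are described as withdrawals and failed contacts, and no deaths are named among them. Twelve-month mortality after hip fracture is described as high, and incapacity ends data collection unless capacity returns.

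The stake is the power statement. If fewer than 79% give a 52-week NEADL, the trial has fewer than the 352 completers on which the 90% rests. The internal pilot cannot reveal this, because it ends about 26 weeks after the first site opens and nobody can then have reached week 52.

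**Working it through.** **Inputs.** From section 11.2: difference 2.4, SD 10, R² 0.52, alpha 5% (taken as two-sided, since the sidedness is not stated), power 90%, retention 79%. From section 4: 1:1 allocation.

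**Step 1: the plan's own figures.**
- Residual SD = 10 × √(1 − 0.52) = 6.928.
- Number per arm = 2 × (1.960 + 1.282)² × 48 / 2.4² = 175.1, rounded up to 176, so 352 in total.
- Number to recruit = 352 / 0.79 = 445.6, rounded up to 446.

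Both figures reproduce.

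**Step 2: where the 79% comes from.** 62 − 9 − 4 = 49, and 49/62 = 79.0%. This is the proportion followed up at 3 months.

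**Step 3: power of 446 under other 52-week retention rates.** The protocol gives no 52-week rate, so every value of r below is an assumption. Completers = 446 × r. Power = Φ(2.4 / (6.928 × √(4 / completers)) − 1.960). The last column is 352 / r rounded up, the number that would have to be recruited to keep 352 completers.

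| Assumed 52-week retention | Completers from 446 | Power | Recruits needed for 352 completers |
|---|---|---|---|
| 79% | 352 | 90.2% | 446 |
| 75% | 334 | 88.6% | 470 |
| 70% | 312 | 86.4% | 503 |
| 69% | 308 | 86.0% | 511 |
| 65% | 290 | 83.9% | 542 |
| 60% | 268 | 80.9% | 587 |

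A noncentral t calculation gives values 0.2 to 0.3 points lower, for example 88.5% at 75% and 80.6% at 60%. Power drops below 88% once retention is under about 73.5%, and below 80% once it is under about 58.7%.

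**Step 4: what the pilot can see.** The pilot window is 6 months, about 26 weeks, and the endpoint is at 52 weeks. The pilot can therefore measure early retention only, whatever its result.

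**The case against.** The strongest reply is that nothing has been shown to be miscalculated. The documents fix no 52-week retention, and if 79% is achieved the power statement is right. That stands. A reader might infer that 446 is a wrong number or that the trial is underpowered, and the protocol does not support either claim. It supports only that the 90% is conditional on an unjustified assumption.

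A second tempting step is to multiply the 79% by survival at the lowest cited mortality, 14%. This is not sound. The 14 to 58% covers the whole 12 months, so applying it after month 3 counts early deaths that fall before randomisation or are already part of the early losses. It also describes hip fracture patients in general. The trial excludes care-home residents and people lacking capacity, and section 3.2.3.2 reports that the unselected cohort was older and more likely to die than the feasibility trial's patients. The mortality figures indicate direction and cannot fix the size.

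Third, the pilot's 69% Go level might look like an error because it lies below 79%. It equals the lower confidence limit quoted in the same section, and a progression floor need not equal the planning value. The recruitment Go level of 2 per site per month is likewise below the 3.25 target. How many participants would be assessable in the pilot depends on a site-opening schedule that the protocol does not give, so no argument is built on that.

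There is also some slack. One feasibility withdrawal came before baseline, and here baseline must precede randomisation; without that patient the rate is 49/61 = 80%. Section 11.3 plans multiple imputation where appropriate, and an observed 17-week NEADL could recover part of the information from later losses, though in general not all of it. The SD of 10 is larger than the 5.8 seen in the feasibility trial, but section 11.2 justifies that by a more diverse sample, not as a reserve for attrition. Finally, the IDSMC meets at least annually and reviews trial conduct (section 15.3.3), so the pilot is not the only oversight. These points moderate the consequence. None of them supplies the missing 52-week assumption.

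**Conclusion.** The concern holds as a gap in justification. Section 11.2 uses a 3-month retention rate as if it were a 52-week rate, without saying so, while other parts of the same protocol make further loss after month 3 likely. The division itself is correct.

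The size is conditional and modest. Relative to 90%, the shortfall is about 1.5 points at 75% retention, about 4 points at 69 to 70%, about 6 at 65% and about 9 at 60%. These values rest on the plan's difference, SD and R², on a two-sided 5% test, on 52-week completers only, and on assumed retention rates that the protocol does not give. Power remains above 80% down to about 59% retention. No estimate, test or allocation rule is affected, so this is something that should be fixed and does not threaten the design.

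**What to change.** In section 11.2:
- Say that the 79% was observed at the feasibility trial's 3-month follow-up.
- State the retention assumed at 52 weeks and the reason for it, covering death, loss of capacity and withdrawal after month 3.
- Restate the power of 446 over a plausible range, for example: 90% if 79% provide a 52-week NEADL, and about 88% at 75%, 86% at 69 to 70%, 84% at 65% and 81% at 60%.

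In section 4, add a sentence saying that the pilot's retention criterion reflects early retention only and does not confirm the 52-week assumption.

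The cost is protocol wording and a power statement that may read slightly less favourably. No extra patients are required. If the sponsor prefers to keep 90% power at a lower assumed retention, the last column of the table gives the corresponding recruitment, for example 511 at 69%.

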11.2.1 Feasibility (attaining recruitment targets)

The phase II trial has provided estimates of the recruitment and retention rates. In a nine-month period between June 2014 and March 2015, 593 patients with proximal femoral fracture were screened for eligibility, of which 266 (45%) were eligible. The main reason for ineligibility was lack of mental capacity (49%). Out of those eligible 193 (73%) were invited to participate and 62 (32% of the eligible population who were invited) agreed to participate. So to recruit 446 we would need to invite 1,394 who are eligible to participate and screen 3,097 patients with proximal femoral fracture. In order to do this we will aim to recruit 12 sites in six geographical locations: Merseyside, North Wales, South Wales, Nottingham, London and East Anglia and recruit participants over 14 months.

11.3 Analysis Plan

A fully documented Statistical Analysis Plan (SAP) will be written and agreed by CTRC statistical team and the IDSMC before data collection has been completed.

Descriptive statistics will be used such as recruitment and retention rates. Normally distributed outcome and process measure scores will be reported as mean scores with their standard deviations at baseline and at follow-up after 17 and 52 weeks. Medians and interquartile ranges will be used for skewed outcome measure data. Differences between hospitals will be presented for all outcomes.

Analysis will be conducted on an intention to treat basis, blind to treatment allocation. The main analysis for primary and continuous secondary outcomes at 17 and 52 weeks will be an analysis of covariance (ANCOVA) adjusted for baseline score, allocation group and stratification variables. The aim is to minimise missing data; however, predictors of missing data will be investigated using

regression models and any significant predictors will be considered for inclusion in the models. Multiple imputation will be employed to address missing scores where appropriate. Analysis of complete case data will be completed as a sensitivity analysis to establish the sensitivity of the treatment effect estimates to the missing data. In addition, given the two assessment points at 17 and 52 weeks, we will carry out a sensitivity analysis using a joint modelling approach to check whether there is any difference in outcome (here the longitudinal outcome rather than the outcome at 17 weeks or 52 weeks alone) between the randomised arms adjusted for dropout or missingness. All treatment effect estimates will be presented with 95% confidence intervals. Sub-group analysis will be planned *a priori* and will be included in the statistical analysis plan. It will include a Complier Average Causal Effect (CACE) analysis based on a number of characteristics decided *a priori*, which will include variables such as the number of therapy sessions received.

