7.6 Randomisation Procedures

Participants will be randomised by a delegated member of the research team. The randomisation will have an allocation ratio of 1:1 within each stratum and across the trial. Participants will be stratified by: (1) site and (2) gender. Randomisation is completed by secure web access to the remote randomisation site at the CTRC.

Participants will be randomised to receive either the enhanced rehabilitation intervention or usual rehabilitation care (in a ratio of 1:1) once:

- a. Eligibility criteria have been confirmed;
- b. Fully informed written consent has been obtained;
- c. Baseline assessments have been completed.

A personal login username and password, provided by the CTRC, will be required to access the randomisation system; designated research staff will be issued with their personal login and password.

When the system requirements (eligibility, consent, and baseline assessment) are confirmed, the participant treatment allocation and a unique trial number will be displayed on a secure webpage and an automated email confirmation will be sent to the authorised randomiser, Principal Investigator (PI) and trial coordinator. A blinded copy of the randomisation email may also be sent to the relevant RPSO.

Randomisation: web access http://ctrc.liv.ac.uk/Randomisation/Femur3

If there are any problems with the randomisation systems contact the coordinating CTU on [name] or via email on [contact]

(Note that the coordinating CTU is open from 0900 – 1700, Monday – Friday, excluding public holidays)

In the event of a randomisation system failure, the site should contact the coordinating team in CTRC (Monday to Friday between 9:00 to 17:00 excluding bank holidays) to try to resolve the problem. If the problem cannot be resolved, the coordinating CTRC will perform central randomisation and randomise the participant using the back-up randomisation system or advise the site to randomise when the randomisation system is live. The back-up randomisation system is an exact replica of the live system but is based on a standalone PC at CTU.

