9.1.1 Baseline

Baseline should be recorded up-to 4 weeks after surgery, in line with timings for obtaining consent.

Participants: Data collection at baseline will include (but not limited to) type of hip fracture, comorbid conditions, Date of surgery, type of surgery, prior living arrangements/place of residence.

Questionnaires administered at baseline will be NEADL, HADS, AMTS, VAS hip pain intensity, FES-I, VASFoF, EQ-5D-3L questionnaire, CSRI, Grip strength.

Carers: Care-giver CSI and care-giver HADS

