11.4 Procedures for Assessing Effectiveness

Effectiveness will be determined comparing patient-completed NEADL scale scores at 52 week follow-up between the two intervention groups.

Nottingham Extended Activities of Daily Living (NEADL) Scale³⁵

This is a patient-completed outcome measure of activities of daily living from the previous 4 weeks which has evidence of validity in stroke patients. The NEADL is a record of actual activity rather than capability, scoring patients in the areas of mobility, kitchen, domestic and leisure activities. A higher score indicates a greater level of independence. When assessed at baseline, it will assess the participant's functional capacity prior to hip fracture. When NEADL is administered the patient will be asked to recall the 4 weeks prior to hip fracture and not 4 weeks prior to completing this questionnaire. It will also be used at the 17 and 52-week follow-up assessment to assess the degree of functional recovery. The score range is 0 to 66 with higher scores indicating greater independence.

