11.5 Secondary Objectives of Cost-Effectiveness and Mechanisms/Processes

Patient completed measures - secondary outcome

Hospital Anxiety and Depression Scale (HADS)³⁶

This is a patient-completed outcome measure of anxiety and depression. It is designed to measure anxiety and depression in patients with physical health problems. It has seven items related to common symptoms of anxiety and seven for depression. Patients are asked whether they experience the symptom definitely, sometimes, not much or not at all. The HADS was designed for use in the hospital setting but has been used successfully with the general population. This measure will be used at baseline and at the 17 and 52 week follow-up assessment. The two sub-scales have a range of 0 to 21 with higher scores indicating increased anxiety or depression.

Process measures

Abbreviated Mental Test Score (AMTS)³³.

The AMTS is a test with evidence of validity that is widely used in clinical and research settings in the UK for detecting and monitoring cognitive impairment. This will be used as a baseline description of the level of cognition. It is brief (ten items) and recommended for cognitive screening in acute settings in the Alzheimer's Society (2013) tool-kit³⁴ 'Helping you to assess cognition: a practical toolkit for clinicians'. It is generally considered to be easily administered and well tolerated by raters and subjects. This measure will be used at baseline and at the 17 and 52 week follow-up assessments. The score range is 0 to 10 with higher scores indicating worse cognitive function.

Visual Analogue Scale (VAS) for hip pain intensity³⁷

This is a patient-completed VAS of current hip pain intensity. Hip pain following surgery is an important factor affecting rehabilitation and will be measured at baseline and at the 17 and 52 week follow-up assessment. We have chosen a VAS as there is evidence of validity compared with the Oxford Hip Score whilst being simpler and quicker to complete, thus reducing the burden on patients. The range is 0 to 10 on a segmented line.

Falls Efficacy Scale - International (FES-I) (self efficacy)^{38,39}

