The FES-I measures how concerned a patient is about falling when performing activities of daily living both inside and outside of the home. The scale details 16 activities which the patient must rate from 1 (not at all concerned) to 4 (very concerned) with regards to how concerned they would be about falling if they performed the activity. The range is 16 to 64 with higher scores indicating a greater fear of falling. The FES-I has been used successfully in older patients both without and with mild cognitive impairment and will be used to measure fear of falling in our trial at baseline, 17 and 52 week follow-up.

Visual Analogue Score - Fear of Falling (VASFoF)⁴⁰

This is a patient-completed VAS for fear of falling. A VAS is useful as it is easy to administer and brief. The range is 0 to 10 on a segmented line with higher scores indicating greater fear of falling. It has previously been used in older adults with and without cognitive impairment with good results and will be used to measure fear of falling in our trial at baseline, 17 and 52 week follow-up.

Grip strength⁴⁶

This is an objective measure of physical function that will be administered in a standardised manner by the researcher administering the patient-completed questionnaires. Grip strength correlates well with general fitness and muscle strength relating to physical function^{47,48}. It is also a more appropriate measure for use at baseline, as performing other physical assessments may carry risk to patients at this time point or would be likely to primarily reflect post-operative pain and not overall function. Grip strength will be measured at baseline and at the 17 and 52 week follow-up assessments.

Short Physical Performance Battery (SPPB)^{49,50}

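### The primary ANCOVA is valid, but pre-specifying age, baseline AMTS and baseline grip strength as further covariates would be a near-free improvement

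*Protocol*

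**What the plan says.** Section 11.3 states the model for the primary and continuous secondary outcomes at 17 and 52 weeks: ANCOVA "adjusted for baseline score, allocation group and stratification variables". Section 4 gives the stratification variables: "superiority RCT, with 1:1 allocation ratio, stratified by gender and site".

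On the baseline score, section 11.4 says: "When NEADL is administered the patient will be asked to recall the 4 weeks prior to hip fracture". The covariate therefore describes function before the injury, not the patient's condition at randomisation.

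Section 9.1.1 lists what else is measured: "Questionnaires administered at baseline will be NEADL, HADS, AMTS, VAS hip pain intensity, FES-I, VASFoF, EQ-5D-3L questionnaire, CSRI, Grip strength". Date of birth is recorded under 3.4.3. Section 7.6 makes it a condition of randomisation that "Baseline assessments have been completed". On relevance, 11.5 says of grip strength: "Grip strength correlates well with general fitness and muscle strength relating to physical function", and of AMTS: "This will be used as a baseline description of the level of cognition".

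Section 11.3 leaves one route for other covariates. Predictors of missing data will be explored by regression, and significant ones considered for the models. It also plans multiple imputation where appropriate, a complete-case sensitivity analysis, a joint-modelling sensitivity analysis that allows for dropout, and a separate SAP, which is not at hand.

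**The concern.** Recovery at one year plausibly depends on how the patient is after fracture and surgery as well as on function beforehand. None of the named covariates measures that state directly, although cognition and grip strength are measured in that window and age is known. The protocol treats these domains as relevant: the working theory in 3.2.1 says that physical and mental comorbidity affects the ability to meet rehabilitation goals, and secondary objective 4 (3.3.2) names cognitive and physical function as potential mediators of activities of daily living.

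Two things are at stake. The first is precision on the primary question. The second is missing data. Under 7.2, an AMTS of 8 or less at follow-up triggers a reassessment of capacity, and nothing more is collected until capacity is confirmed. Under 12.2, collection stops if capacity is lost. Declining cognition is thus a cause of missing NEADL by the protocol's own rules, in a trial that plans for 21% attrition. Baseline AMTS is the obvious variable to carry in the analysis and imputation models from the start, rather than leave to a significance test.

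**Working it through.** **Inputs (section 11.2).** Difference 2.4 points, SD 10, R² of covariate 0.52, alpha 5% (taken as two-sided, in line with the 95% intervals in 11.3), power 90%, retention 79%, allocation 1:1.

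**The plan's own figure.**
- Residual SD = 10 × √(1 − 0.52) = 6.928.
- n per arm = 2 × [6.928 × (1.960 + 1.282) / 2.4]² = 175.1, rounded up to 176, so 352 in total.
- Recruited = 352 / 0.79 = 445.6, rounded up to 446.
- With 176 per arm, SE = 6.928 × √(2/176) = 0.739 and power = Φ(2.4/0.739 − 1.960) = 90.1%.

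All stated figures reproduce, so the model and the sample size agree.

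**Adding covariates.** No document gives the variance that age, AMTS and grip strength explain beyond baseline NEADL, site and gender. The total R² below is therefore an assumed range that starts at no gain. The equivalent number of completers under the planned R² is 352 × 0.48 / (1 − R²).

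| Total R² | SE | 95% CI half-width | Power at 352 | Equivalent completers |
|---|---|---|---|---|
| 0.52 (no gain) | 0.739 | 1.45 | 90.1% | 352 |
| 0.54 | 0.723 | 1.42 | 91.3% | 367 |
| 0.57 | 0.699 | 1.37 | 93.0% | 393 |
| 0.60 | 0.674 | 1.32 | 94.5% | 422 |

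Across 0.54 to 0.60 the standard error falls by about 2% to 9%.

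**If the recalled score predicts less well.** An R² of 0.52 implies a correlation of √0.52 = 0.72 between recalled pre-fracture NEADL and NEADL at 52 weeks. Section 11.2 does not say where 0.52 comes from, and the feasibility trial followed patients for three months only (3.2.2). As an assumption, let the new covariates explain 10% of the residual variance:
- Starting R² 0.40: power 82.8%. Adding 0.10 × 0.60 = 0.06 gives R² 0.46 and power 86.5%.
- Starting R² 0.30: power 76.8%. Adding 0.10 × 0.70 = 0.07 gives R² 0.37 and power 81.0%.

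**Cost if they add nothing.** With 352 completers and the planned 12 sites, the stated model uses an intercept, arm, baseline NEADL, gender and 11 site terms, leaving 352 − 15 = 337 residual degrees of freedom. Three linear terms leave 334. Chance imbalance in useless covariates inflates the variance by roughly 3/334 = 0.9%. The SE goes from 0.739 to about 0.742 and power from 90.1% to about 89.9%.

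**The case against.** The strongest reply is that nothing here is an error. ANCOVA on the baseline score and the stratification factors is a standard, valid analysis. It matches the method used for the sample size and already delivers 90% power, and the SAP may name more covariates. All of this stands, and it is why the point is an improvement rather than a fault.

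The size of the gain is also open to challenge. The planned 0.52 refers to a single covariate, so any contribution from site and gender comes on top and is not credited. Grip strength probably overlaps with gender, and age with pre-fracture function. Excluding patients without capacity probably narrows the range of AMTS. The true gain could be near zero, and the assumed range has to include that.

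A third reply is that 11.3 already lets predictors of missing data into the models. So it would be wrong to say that nothing else can enter. But that route depends on a significance test on accrued data and is discretionary. It also screens for association with missingness, not with outcome. It does not fix the primary model in advance and does not aim at precision.

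A reader might go further and infer that the standard error is certainly larger than it need be, or that the complete-case analysis is not credible. The documents support neither. No figure for added R² is given, and the complete-case analysis is only a sensitivity analysis beside multiple imputation and a joint model.

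**Conclusion.** The point holds as a recommended improvement to a valid analysis. There is no bias, and no contradiction with the sample size. Age, baseline AMTS and baseline grip strength are available before allocation and probably prognostic. Leaving them to a data-driven screen for missingness is weaker than fixing them in advance.

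Under the planned R², power at 352 completers lies between 90.1% (no gain) and 94.5% (total R² 0.60). If the recalled score explains less than planned, there is more room to gain. These sizes rest on assumed values of R², SD 10, a two-sided 5% test and 352 completers. The missing-data argument for AMTS does not rest on those figures. It follows from the rules in 7.2 and 12.2, together with the plausible assumption that baseline cognition predicts later loss of capacity.

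**What to change.** In 11.3, give the covariates for the 17- and 52-week NEADL models as baseline NEADL, site, gender, age, baseline AMTS and baseline grip strength. Put the same variables in the imputation model. Fix the list before any outcomes by arm are seen, and keep the shorter model as a sensitivity analysis. Days from surgery to randomisation could be added but is optional: it is capped at four weeks, and the documents give no direct evidence that it is prognostic. Make the change in the protocol as well as the SAP, since the protocol states the model.

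Before AMTS is used, reconcile its scoring direction. Section 11.5 says that higher scores mean worse cognition, whereas 7.2 treats a low score as the warning sign.

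The cost is wording and about three degrees of freedom. No new data are needed, and missing covariate values should be rare because 7.6 requires baseline to be complete before randomisation.
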